### **7.8. Subject Follow-up**

All subjects will undergo a follow-up examination at 30±7 days and at 60±14 days post procedure to assess for any major or minor complications or adverse events. All subjects will be assessed for ipsilateral ankle/brachial index at both follow-up visits. All subjects will undergo a femoral duplex ultrasound exam at the 30-day follow-up. If abnormalities are detected at the 30 day ultrasound based on investigational site review, the test should be repeated at the 60 day assessment.

### **7.9. Ultrasound and Core Lab**

Each site is responsible for performing ultrasound examinations according to the ultrasound Core Laboratory imaging protocol. All ultrasound images will be transferred to and evaluated by a Core Lab. All ultrasound data will be produced by the Core Lab according to standard criteria established by the Core Lab. If necessary for comparison purposes, baseline CTA images will also be provided to the Core Lab for assessment; these will be requested from the investigational sites as needed.

It is the responsibility of each site to perform the local interpretation of the ultrasound examination for clinical assessment. The Core Lab will not be responsible to notify the site of any abnormal findings that are identified in the study. The responsibility of the Core Lab is to complete the data collection forms and submit these to the Sponsor. Data obtained from the core lab readings will be used for study purposes only and not for clinical treatment of the subject. Essential Medical will use only the measurements provided by the Core Lab for analysis. If the Core Lab determines that the data are unreadable, the site will be responsible for having the subject return for another assessment.

## 8 Statistical Methods

### 8.1. Study Hypotheses

#### 8.1.1 Effectiveness

The primary and secondary effectiveness analyses will be performed on both the Primary Analysis dataset (all Analysis Cohort subjects with an attempt to treat and having an assessment of the primary effectiveness parameter) and the Per-Protocol dataset (subjects from the Intent-to-Treat dataset with no major protocol violations). Results based on the Primary Analysis and the Per-Protocol datasets will be presented in the clinical report. Differences between the results will be examined. All primary and secondary effectiveness parameters will be analyzed. Roll-in subjects will be analyzed separately from the Analysis Cohort.

The primary effectiveness hypothesis is that mean Time to Hemostasis is less than the Performance Goal of 10 minutes, as follows:

$H_0: \mu \geq 10$   
vs.  
 $H_A: \mu < 10,$

where  $\mu$  is the population mean Time to Hemostasis.

The secondary endpoints are as follows:

1. Technical Success
2. Ambulation Success
3. Time to Ambulation
4. Treatment Success
5. Procedure Time

Technical Success, Ambulation Success, Time to Ambulation, Treatment Success and Procedure Time will be analyzed and reported but there will be no formal statistical test on these endpoints.

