### **8.3.3 Final Analysis**

The primary effectiveness endpoint, Time to Hemostasis, will be tested by placing an exact one-sided upper 97.5% confidence bound on the mean Time to Hemostasis. If this upper confidence bound is less than 10 minutes the study will have met its primary effective objective. Time to Hemostasis will not be truncated. In the event that Time to Hemostasis cannot be evaluated because a surgical repair must be performed, Time to Hemostasis for that subject will be imputed using the longest Time to Hemostasis from any subject for whom that datapoint exists. There are no statistical tests of the secondary effectiveness endpoints.

The crude rate of the primary safety endpoint, Major Complications, will be presented as the proportion of subjects with one or more Major Complications, along with its exact one-sided upper 97.5% confidence bound. If a significant number of subjects are lost to follow-up or die due to a reason other than a major complication, the Major Complication rate will also be estimated as a Kaplan-Meier rate. Subjects lost to follow-up will be censored at the date of their last contact. Subjects who die due to a reason other than a Major Complication will be censored at their date of death. An exact one-sided upper 97.5% confidence bound will be placed on the estimated major complication rate at 30 days using the formula given by Peto, Peto, and Armitage. If this upper confidence bound is less than 19.9%, the study will have met its primary safety objective. In addition, the proportion of subjects with each individual Major Complication will be presented along with their two-sided exact 95% confidence intervals.

The secondary safety endpoint, Minor Complications, will be presented as the proportion of subjects with one or more Minor Complications. Minor Complications will be qualitatively assessed against a Clinical Acceptance Criterion of 20%. This CAC will not be statistically tested.

VARC-2 Major Vascular Complications will be reported as another second safety endpoint but will not be statistically tested against a PG or qualitatively assessed against a CAC.

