### **8.3.6 Missing Data**

It is highly unlikely that there will be missing data for Time to Hemostasis, Technical Success, Ambulation Success, Time to Ambulation, Treatment Success or Procedure Time. However, if any of these endpoints are missing, the worst value observed for any subject at the same study site will be imputed for the missing value.

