4.1 Primary Analysis Cohort

The Primary Analysis Cohort (PAC) will consist of all non-roll-in subjects in whom an attempt to use the device was made (i.e., subjects who sign the consent form but are deemed ineligible for the study prior to any attempt to use the MANTA device will not be included in the efficacy analyses). Subjects who are excluded due to intra-procedural exclusions will be excluded from the efficacy analyses as long as the MANTA sheath has not been introduced; use of the MANTA puncture locator at the beginning of the procedure is not considered "attempted use" of the MANTA device.

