5 DATA CONVENTIONS AND DEFINITIONS

5.1 Handling of Missing Data

Missing data will not be imputed for safety endpoints. However, if more than 13 subjects in the Primary Analysis Cohort either die for a reason other than a Major Complication or are lost to follow up within 30 days of treatment, then the rate of Major Complications will also be estimated by the Kaplan-Meier method, to allow for subjects who are censored before a Major Complication can be observed. See Section 2.4.1 for further details.

For effectiveness endpoints, it is highly unlikely that there will be missing data for Time to Hemostasis, Technical Success, Ambulation Success, Time to Ambulation, Treatment Success or Procedure Time. However, if any of these data are missing (i.e., in the event that Time to Hemostasis cannot be evaluated because a surgical repair must be performed), the worst value observed for any subject at the same study site within each analysis cohort, will be imputed for the missing value. Missing data for a subject in the Primary Analysis Cohort will be imputed with the worst value observed for any Primary Analysis Cohort subject at the same study site, and missing data for a subject in the Roll-In Cohort will be imputed with the worst value observed for any roll-in subject at the same study site.

No other imputations will be carried out for missing data.

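### Protocol 8.1.1 requires an assessed Time to Hemostasis for the primary effectiveness dataset, which contradicts the imputation rules and the SAP's cohort defined by attempted use

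*Protocol*

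**What the plan says.** Protocol 8.1.1 runs the primary and secondary effectiveness analyses on a Primary Analysis dataset of "all Analysis Cohort subjects with an attempt to treat and having an assessment of the primary effectiveness parameter". Two conditions apply jointly: an attempt and an assessment. The safety set in Protocol 8.1.2 needs only an attempt. Section 8.1.1 draws the Per-Protocol set as "subjects from the Intent-to-Treat dataset with no major protocol violations", but neither document as supplied defines an Intent-to-Treat dataset.

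Protocol 8.3.3 provides for a missing primary outcome: "In the event that Time to Hemostasis cannot be evaluated because a surgical repair must be performed", then "Time to Hemostasis for that subject will be imputed using the longest Time to Hemostasis from any subject for whom that datapoint exists". Protocol 8.3.6 has a general rule covering TTH and the secondary effectiveness endpoints, under which "the worst value observed for any subject at the same study site will be imputed for the missing value".

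SAP 2.4.2 states the effectiveness hypothesis for the Primary Analysis Cohort, which under SAP 4.1 "will consist of all non-roll-in subjects in whom an attempt to use the device was made". No assessed TTH is required. SAP 5.1 gives the surgical case as its example of missing data ("in the event that Time to Hemostasis cannot be evaluated because a surgical repair must be performed") and imputes the worst value at the same site within the same cohort. Under SAP 4.2, missing TTH removes a subject from the Per Protocol Set only. SAP 8 lists no changes in the planned analyses.

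**The concern.** A TTH that cannot be evaluated is, in ordinary language, not an assessment. On that reading 8.1.1 removes the very subjects for whom 8.3.3 and SAP 5.1 supply a value. Both documents name surgical repair as the reason a TTH would be unevaluable, and Protocol 7.6 lists surgery among the rescue measures when bleeding control fails. Missingness is therefore tied to closure failure. In a single-arm test against a fixed 10-minute goal, leaving such subjects out lowers the tested mean.

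The literal reading has two further consequences. First, the same dataset serves the secondary effectiveness endpoints. A subject needing unplanned surgery is by definition not a Technical Success, yet would leave that denominator if TTH was not evaluable. Second, the planned comparison with the Per-Protocol result could not expose the problem, because SAP 4.2 already removes missing TTH from that set.

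**Working it through.** **The texts side by side, for a subject with attempted use, surgical repair and no evaluable TTH**

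| Place | Treatment of this subject |
|---|---|
| Protocol 8.1.1 | Outside the primary dataset, read literally |
| Protocol 8.3.3 | Imputed: longest TTH of any subject |
| Protocol 8.3.6 | Imputed: worst value at the same site |
| SAP 4.1 and 5.1 | In the cohort; worst same-site value in that cohort |
| SAP 4.2 | Out of the Per Protocol Set only |

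**The plan's own figure.** Protocol 8.2 gives 62 subjects for 80% power: mean 6 against 10 minutes, SD 11, one-sided 0.025. The normal approximation is (11 × (1.960 + 0.842) / 4)² = 59.4, so 60. The one-sample t-test (noncentral t) gives power of 79.8% at 61 and 80.45% at 62. The figure of 62 reproduces, and the choice of analysis set does not alter it.

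**Illustration.** The inputs are:
- N = 263 treated (Protocol 8.2). TTH is measured at the procedure, so later loss to follow-up does not reduce it.
- Evaluable subjects have mean m = 6 and SD s = 11 (Protocol 8.2), or alternatively 2.38 and 6.63 minutes (EU study, Protocol 1.4: 2 min 23 s and 6 min 38 s).
- The number k of unevaluable subjects and the imputed value M are assumptions, since the documents give neither. M = 37.2 minutes is the EU study's longest time (37 min 10 s); 60 and 120 are chosen to show the range.

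Dropped: bound = m + t(0.975, N−k−1) × s / √(N−k).

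Imputed: mean = ((N−k)m + kM) / N, and SS = (N−k−1)s² + (N−k)(m − mean)² + k(M − mean)². The bound is mean + t(0.975, N−1) × √(SS/(N−1)) / √N.

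Worked case, design values, k = 11, M = 60:
- Mean = (252 × 6 + 11 × 60) / 263 = 8.26.
- SS = 251 × 121 + 252 × 2.26² + 11 × 51.74² ≈ 61,100.
- SD = √(61,100/262) ≈ 15.27, and SE = 15.27/√263 ≈ 0.942.
- Bound = 8.26 + 1.969 × 0.942 = 10.11.
- With the 11 dropped: 6 + 1.969 × 11/√252 = 7.36.

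Smallest k at which imputation misses the goal, N = 263:

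| Evaluable subjects | M (min) | k | Share | Bound, imputed | Bound, dropped |
|---|---|---|---|---|---|
| 6 / 11 | 37.2 | 20 | 7.6% | 10.00 | 7.39 |
| 6 / 11 | 60 | 11 | 4.2% | 10.11 | 7.36 |
| 6 / 11 | 120 | 5 | 1.9% | 10.48 | 7.35 |
| 2.38 / 6.63 | 37.2 | 45 | 17.1% | 10.09 | 3.27 |
| 2.38 / 6.63 | 60 | 25 | 9.5% | 10.05 | 3.23 |
| 2.38 / 6.63 | 120 | 11 | 4.2% | 10.27 | 3.21 |

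Below these counts both treatments meet the goal. Under design values with M = 37.2, the imputed bound is 7.47 at k = 1, 8.01 at k = 5 and 9.08 at k = 13, against 7.34 to 7.37 when dropped.

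**The case against.** The strongest reply is that the documents largely settle the matter. The SAP chain is unbroken: hypothesis in the Primary Analysis Cohort (2.4.2), cohort by attempted use (4, 4.1), surgical case imputed (5.1). Protocol 8.3.3 and 8.3.6 impute as well. One general parenthesis in 8.1.1 stands against specific rules in both documents, and an imputed value might be counted as an assessment. This stands as evidence of intent. It does not remove the contrary wording, which sits in the protocol's definition of its primary dataset and which SAP 8 does not acknowledge.

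Three stronger readings are tempting and not supported:

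- A reader might infer that the sponsor will drop closure failures. The specific rules point the other way, and subjects with long but recorded times stay in under either definition.
- A reader might infer that 8.1.1 empties all the imputation rules. It would empty only those for TTH; 8.3.6 would still serve the other effectiveness endpoints for subjects whose TTH was assessed.
- A reader might take the EU study as a measure of the bias. Its 3 failures took 37.17 + 27 + 13 = 77.2 of 50 × 2.383 = 119.2 minutes (64.8%), and without them the mean is (119.2 − 77.2)/47 = 0.89 instead of 2.38. Those three had recorded times, so 8.1.1 would keep them. The figures show only that a few long times can dominate a mean.

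**Conclusion.** The contradiction is real and should be corrected. The confidence attaches to the textual conflict; actual exclusion of these subjects is not established.

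The effect on the trial's conclusion depends on two quantities the documents do not give: how many subjects have unevaluable TTH, and what value is imputed. Under the design assumptions the choice of dataset can reverse the result at 1.9% to 7.6% of 263 subjects, over imputed values from 120 down to 37.2 minutes. If performance resembles the EU study, that takes 4.2% to 17.1%. With few such subjects both definitions meet the goal. The calculation applies the design mean and SD to evaluable subjects only. If the sponsor meant them to cover failures too, evaluable subjects would do better and the illustration overstates the effect.

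Aligning the populations alone would leave the tested mean unsettled. Protocol 8.3.3 and SAP 5.1 give the surgical case different values. The worst same-site value can be short, and it can be absent at a site with one subject, since Protocol 8.4 sets no minimum per site.

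**What to change.** 1. Delete the assessment condition in Protocol 8.1.1, or state in SAP 8 that SAP 4.1 governs. Either way, the primary effectiveness set becomes all non-roll-in subjects with attempted use.
2. State one imputation rule for unevaluable TTH in Protocol 8.3.3, Protocol 8.3.6 and SAP 5.1. The rule in 8.3.3 (longest TTH of any subject) is the more conservative, and it still yields a value where a site has no other subject.
3. In Protocol 8.1.1, replace the reference to an Intent-to-Treat dataset with the Primary Analysis Cohort, as SAP 4.2 already has it.
4. Record the alignment in SAP 8.

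No new data and no change in sample size are needed: 62 stands for effectiveness, and the total is driven by safety. The mean may come out less favourable. A protocol edit must go through the approvals in Protocol 14.1. The SAP route is lighter for the dataset definition, provided it also settles the imputation rule.

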#### 8.1.2 Safety

The primary and secondary safety analyses will be performed on all enrolled study subjects in the Analysis Cohort in whom an attempt to use the device is made (i.e., subjects who sign the consent form but are deemed ineligible for the study prior to any attempt to use the MANTA device will not be included in the safety analysis). In addition all adverse events recorded during the study will be summarized, and severity and relatedness to the device and/or procedure will be reported. Roll-in subjects will be analyzed separately from the Analysis Cohort. The primary safety endpoint is Major Complications, as defined in Section 4.

The primary safety hypothesis is that the Major Complication rate (proportion of subjects with one or more Major Complications) is less than the Performance Goal of 19.9%, as follows:

$H_0: \pi \geq 0.199$   
vs.  
 $H_A: \pi < 0.199,$

where  $\pi$  is the population Major Complication rate.

The secondary safety endpoint is Minor Complications. Minor Complications will be qualitatively assessed against a Clinical Acceptance Criterion of 20%. This CAC will not be statistically tested.

VARC-2 Major Vascular Complications will be reported as another second safety endpoint but will not be statistically tested against a PG or qualitatively assessed against a CAC.

## **8.2. Sample Size Considerations**

The population Time to Hemostasis is assumed to be 6 minutes, with a standard deviation of 11 minutes. Based on these assumptions, 62 subjects will provide 80% power to reject the primary effectiveness hypothesis at a one-sided significance of 0.025.

The population Major Complication rate is assumed to be 13%. Based on this assumption, 250 subjects will provide 80% power to reject the primary safety hypothesis at a one-sided significance of 0.025. Therefore, the necessary sample size is driven by the primary safety endpoint and is 250 subjects.

To ensure an adequate sample size of subjects meeting the 30-day primary safety endpoint in case of losses to follow-up (estimated to be 5%), the study will treat a total of 263 subjects.

## **8.3. Data Analysis**

### **8.3.1 Endpoints**

The following Effectiveness Endpoints will be evaluated for the MANTA device, definitions are provided in Section 4 above:

1. Time to Hemostasis (Primary)
2. Technical Success (Secondary)
3. Ambulation Success (Secondary)
4. Time to Ambulation (Secondary)
5. Treatment Success (Secondary)
6. Procedure Time (Secondary)

The following Safety Endpoints will be evaluated for the MANTA device, definitions are provided in Section 4 above:

1. The percentage of subjects with one or more Major Complications within 30 days following procedure (Primary)
2. The percentage of subjects with one or more Minor Complications within 30 days following procedure (Secondary)
3. The percentage of subjects with one or more VARC-2 Major Vascular Complications within 30 days following procedure (Secondary)

### **8.3.2 Interim Analysis**

No formal interim analysis is planned.

### **8.3.3 Final Analysis**

The primary effectiveness endpoint, Time to Hemostasis, will be tested by placing an exact one-sided upper 97.5% confidence bound on the mean Time to Hemostasis. If this upper confidence bound is less than 10 minutes the study will have met its primary effective objective. Time to Hemostasis will not be truncated. In the event that Time to Hemostasis cannot be evaluated because a surgical repair must be performed, Time to Hemostasis for that subject will be imputed using the longest Time to Hemostasis from any subject for whom that datapoint exists. There are no statistical tests of the secondary effectiveness endpoints.

The crude rate of the primary safety endpoint, Major Complications, will be presented as the proportion of subjects with one or more Major Complications, along with its exact one-sided upper 97.5% confidence bound. If a significant number of subjects are lost to follow-up or die due to a reason other than a major complication, the Major Complication rate will also be estimated as a Kaplan-Meier rate. Subjects lost to follow-up will be censored at the date of their last contact. Subjects who die due to a reason other than a Major Complication will be censored at their date of death. An exact one-sided upper 97.5% confidence bound will be placed on the estimated major complication rate at 30 days using the formula given by Peto, Peto, and Armitage. If this upper confidence bound is less than 19.9%, the study will have met its primary safety objective. In addition, the proportion of subjects with each individual Major Complication will be presented along with their two-sided exact 95% confidence intervals.

The secondary safety endpoint, Minor Complications, will be presented as the proportion of subjects with one or more Minor Complications. Minor Complications will be qualitatively assessed against a Clinical Acceptance Criterion of 20%. This CAC will not be statistically tested.

VARC-2 Major Vascular Complications will be reported as another second safety endpoint but will not be statistically tested against a PG or qualitatively assessed against a CAC.

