Cachexia: Defined as very thin, or body mass index  $< 20$  kg/m^2.

Device Deficiency: Inadequacy of a medical device with respect to its identity, quality, durability, reliability, safety or performance; includes device malfunctions, use errors and inadequate labeling.

Echymosis: An area of subcutaneous discoloration caused by the extravasation of blood into the subcutaneous tissue not associated with a definable, palpable subcutaneous mass.

Hematoma: An expanding or non-expanding subcutaneous mass of blood greater than 2 cm in its longest axis, confirmed by ultrasound.

Hemostasis: Cessation of common femoral artery bleeding as determined by visual inspection. Cutaneous or subcutaneous oozing that is readily treated by light compression methods (sand bags and light manual pressure) which do not apply sufficient compression of the femoral artery to control arterial bleeding is considered to meet the definition of hemostasis.

Major Complications:

- i. Vascular injury attributable to the MANTA device requiring surgical repair or stent-graft;
- ii. Access site-related bleeding that is attributable to failure of or sub-optimal performance of the MANTA device and that results in transfusion;
- iii. New onset ipsilateral lower extremity ischemia that originates with the common femoral artery, is attributable to the MANTA device, causes a threat to the viability of the limb, and requires surgical repair or additional percutaneous intervention;
- iv. Access site-related nerve injury attributable to the MANTA device that is permanent (lasting >30 days) or requires surgical repair; and
- v. Access site-related infection requiring intravenous antibiotics and/or extended hospitalization.

Major Vascular Complications: Adapted from the VARC-2 Clinical Guidelines [6]:

- Access site or access-related vascular injury (dissection, stenosis, perforation, rupture, arterio-venous fistula, pseudoaneurysm, hematoma, irreversible nerve injury, compartment syndrome, percutaneous closure device failure) leading to death, life threatening or major bleeding,\* visceral ischemia, or neurological impairment OR
- Distal embolization (noncerebral) from a vascular source requiring surgery or resulting in amputation or irreversible end-organ damage OR
- The use of unplanned endovascular or surgical intervention associated with death, major bleeding, visceral ischemia or neurological impairment OR

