#### Monitoring Time to Hemostasis

Time to Hemostasis is measured from the time the MANTA sheath is withdrawn from the artery until first observed and confirmed arterial hemostasis. As Time to Hemostasis is a primary endpoint for this study, it is critical to measure it accurately. If manual or mechanical compression is required, every attempt should be made to check for hemostasis as frequently as logistically and medically possible to obtain accurate Time to Hemostasis. It is important to declare hemostasis within 1 minute after it is achieved. Time to Hemostasis should be inclusive of any time that manual or mechanical pressure is applied (excluding light digital or mechanical pressure to treat oozing).

The following is a suggested, but not required, method for managing arterial bleeding: If hemostasis is not immediate upon deployment, apply manual pressure and check the access site for hemostasis at approximately one minute increments following sheath withdrawal through 10 minutes, and then at approximately two-minute intervals through 20 minutes, until hemostasis. If hemostasis is not achieved by 20 minutes, the access site should be managed per medical judgement inclusive of use of a contralateral balloon or mechanical compression device. A checking interval of 5 minutes is recommended in these cases if deemed medically appropriate.

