#### Treatment of Oozing/Continued Bleeding

- Oozing that is controllable with compression bandages, sand bags or light manual pressure is subcutaneous in origin. Light manual compression may be substituted with light compression applied by a mechanical compression device.
- Bleeding which is not controlled by light manual compression should be controlled by compression of the femoral artery via mechanical or manual compression.
- If necessary, balloon occlusion from the contralateral access site may be performed; such balloon occlusion will not be considered an unplanned intervention.
- Failing these steps, rescue measures may include placement of a stent-graft at the access site or surgical intervention.

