6.2.3 Procedural and Discharge Data

The secondary endpoints are defined below. Summary statistics will be reported for each endpoint, but there will be no formal statistical test performed. Continuous variables will be summarized using descriptive summary statistics such as mean, median, standard deviation, minimum and maximum. Categorical variables will be summarized as counts and percentages. Procedure sheath size, index device, index device size, MANTA size, target artery, target artery diameter, pre-deployment ACT, pre-deployment blood pressure, use of adjunctive methods for hemostasis or oozing, thrombus, and post-deployment angiogram results will also be summarized by endovascular procedure.

Effective puncture size (EPS) (mm): Derived from the combination of procedure sheath brand/size and index device/size, based on an algorithm developed by the sponsor. The algorithm is attached in Appendix B.

Endovascular procedure type: As completed on the eCRF, either TAVI, EVAR, Impella, or Other.

Procedure sheath brand: Derived from the sheath size/brand from the eCRF.

Procedure sheath size (F): As completed on the eCRF.

Index device manufacturer/brand: Derived from the Large Bore Device Used: Brand and Manufacturer from the eCRF.

Index device size (mm): As completed on the eCRF as Large Bore Device Used: Size (units).

MANTA size: As completed on the eCRF, either 18F or 14F.

Target artery: As completed on the eCRF, either Left Common Femoral Artery or Right Common Femoral Artery.

Target artery diameter (mm): As completed on the eCRF as recorded from baseline CTA.

Sheath to femoral artery ratio (SFAR): Calculation is as follows: $(EPS / 3.0)mm / (\text{target artery diameter})mm$

Pre-deployment ACT (sec): As completed on the eCRF.

Pre-deployment systolic and diastolic blood pressure (mmHg): As completed on the eCRF.

Use of adjunctive methods to obtain arterial hemostasis: Instances of need for adjunctive methods to achieve arterial hemostasis summarized by method, either manual compression, contralateral balloon, mechanical device, stent-graft, surgical repair, or other.

Use of adjunctive methods for treating oozing: Instances of subcutaneous oozing summarized by treatment, either light manual pressure, light mechanical pressure, sand bag, pressure dressing, or other.

Any thrombus observed on the MANTA components: As completed on the eCRF as whether thrombus was observed after removal, yes or no, and which component(s) were affected.

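### A stent-graft or other rescue that stops the bleeding at a recorded time enters the primary mean Time to Hemostasis as if MANTA had achieved it

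*Protocol*

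**What the plan says.** **Endpoint.** Protocol Section 4 defines hemostasis as "Cessation of common femoral artery bleeding as determined by visual inspection". TTH runs from sheath withdrawal until arterial hemostasis is first seen and confirmed; SAP 2.6.1 and 6.2.1 repeat this. Neither definition asks what stopped the bleeding. Protocol 8.1.1 tests whether "mean Time to Hemostasis is less than the Performance Goal of 10 minutes", and 8.3.3 uses a one-sided 97.5% upper bound on the untruncated mean.

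**Unfavourable values.** Protocol 8.3.3 imputes the longest TTH of any subject when TTH "cannot be evaluated because a surgical repair must be performed". Protocol 8.3.6 imputes the worst value at the same site for any missing TTH. SAP 5.1 places the surgical-repair case under the same-site rule, within cohort. SAP 6.2.1 has no rule.

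**Rescue.** Protocol 7.6 (Treatment of Oozing/Continued Bleeding) moves from compression to contralateral balloon, noting that "such balloon occlusion will not be considered an unplanned intervention". If these fail, "rescue measures may include placement of a stent-graft at the access site or surgical intervention". Major Complication (i) and Technical Success in Section 4 also put stent-graft or endovascular rescue beside surgery. On timing, Protocol 7.6 states: "Time to Hemostasis should be inclusive of any time that manual or mechanical pressure is applied". SAP 6.2.3 tabulates the method used to obtain arterial hemostasis: "either manual compression, contralateral balloon, mechanical device, stent-graft, surgical repair, or other".

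**The concern.** The study's stated purpose is to evaluate MANTA in achieving hemostasis. When MANTA fails and a stent-graft or another closure device seals the artery, the time to that seal measures the rescue. Nothing in either document removes, replaces or marks down such a time, so by the definition it goes into the mean as observed. For stent-graft this follows from the method-neutral definition and the absence of a rule; it is not stated outright.

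Two failures with the same clinical meaning can therefore be scored differently. A surgical repair whose TTH cannot be evaluated receives an unfavourable value, while a stent-graft, or a repair with a clock time, keeps its own. The tested result then depends partly on the operator's choice of rescue and on whether a time was written down, in an unblinded single-arm study (SAP 2.2.2).

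Treatment Success has a related gap. A stent-graft placed for failure to seal counts as a success if TTH was 10 min or less and no listed Major Complication was adjudicated.

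**Working it through.** **1. The plan's own figure.** Protocol 8.2: "The population Time to Hemostasis is assumed to be 6 minutes, with a standard deviation of 11 minutes". The goal is 10 min, so the difference is 4, at one-sided 0.025 and 80% power.
- Normal approximation: n = (11 × (1.960 + 0.842) / 4)² = 59.4, so 60.
- One-sample noncentral t: 61 subjects give 79.8% and 62 give 80.5%. The stated 62 is reproduced.
- With 263 treated, the half-width is 1.969 × 11/√263 = 1.34 min, so a mean of 6 gives a bound of 7.34 min. Power exceeds 99.9%.

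**2. Direction.** A subject's own time cannot exceed the longest recorded time. Keeping it therefore never gives a higher mean than substituting the longest.

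**3. Shift in the mean.** The documents give no rescue frequency or rescue time, so both are assumed. The EU study's three subjects without Hemostasis Success took 37, 27 and 13 min under manual pressure (Protocol 1.4); their average is 77/3 = 25.7, so a rescue time of 25 min is used. The longest EU time was 37 min 10 s. Shift = fraction rescued × (37 − 25):
- 1%: 0.12 min
- 2%: 0.24 min
- 5%: 0.60 min

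**4. Upper bound.** N = 263, with r subjects rescued. The other N − r have mean m and SD s: 6 and 11 under the design assumptions, or 2.38 and 6.63 as in the EU study. Each rescued subject has value T.
- Mean M = [(N − r)m + rT]/N
- Variance V = [(N − r − 1)s² + (N − r)(m − M)² + r(T − M)²]/(N − 1)
- Bound = M + 1.969 × √(V/N)

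Example, design values, r = 11 (4.2%), T = 60: M = (252 × 6 + 660)/263 = 8.26; SD = 15.27; bound = 8.26 + 1.969 × 15.27/16.22 = 10.11.

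| Others | r | Recorded (25 min) | Imputed 37.17 | 60 | 90 | 120 |
|---|---|---|---|---|---|---|
| Design | 5 | 7.72 | 8.01 | 8.62 | 9.52 | 10.48 |
| Design | 11 | 8.18 | 8.82 | 10.11 | 11.94 | 13.84 |
| Design | 16 | 8.56 | 9.48 | 11.32 | 13.87 | 16.49 |
| EU | 5 | 3.70 | 4.03 | 4.72 | 5.71 | 6.73 |
| EU | 11 | 4.29 | 5.00 | 6.40 | 8.32 | 10.27 |
| EU | 16 | 4.78 | 5.78 | 7.74 | 10.38 | 13.05 |

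**5. Break-even.** The imputed value at which the bound reaches 10 min is about 105, 62 and 44 min for 5, 10 and 16 rescues under the design assumptions, and about 214, 125 and 86 min under EU-like values.

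**The case against.** **This is a missing-data rule, not a penalty for surgery.** A reader might infer that every surgical rescue gets a worst-case value and no other rescue can. The documents do not support that. The line runs between evaluable and not evaluable: surgery with a recorded TTH keeps it, and a stent-graft case with a missing TTH is imputed under Protocol 8.3.6 and SAP 5.1. This stands, and it fixes the scope of the point: recorded times produced by a rescue.

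**Balloon.** A reader might infer that the clock may stop at balloon inflation. That is an unlikely reading. For bleeding beyond 20 min, Protocol 7.6 recommends 5-minute checks while a balloon or mechanical device is in use, which presupposes that hemostasis has not been declared. The hemostasis definition tolerates only oozing held by compression too light to control arterial bleeding, and hemostasis must be confirmed. What remains is a small gap in wording: the sentence on pressure time does not name the balloon, which the documents list apart from mechanical compression.

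**Size.** A reader might assume very fast endovascular rescue, say 5 min, and a large bias. The documents give no such time, and Protocol 7.6 puts stent-graft after compression and balloon. Even then the result holds. Starting from 263 subjects with mean 6 and SD 11, moving 13 (5%) from 5 to 37 min adds 13 × 32/263 = 1.58 to the mean, giving 7.58, SD about 12.9 and a bound of about 9.2 min, below the goal.

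**Failures are visible elsewhere.** Rescue time counts in full and untruncated. A stent-graft fails Technical Success, can be a Major Complication and is tabulated by method. The Treatment Success gap also needs a TTH of 10 min or less after earlier steps and an adjudication that no Major Complication occurred. All true, but Technical Success is not tested and the method table is descriptive, so neither corrects the primary mean.

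**Estimand.** Replacing a measured time with another subject's maximum is a choice. Whether the literature behind the 10 min goal scored rescue this way cannot be checked, because Appendix 2 is not in the text available. That is a reason to report both analyses.

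**Conclusion.** The point holds in limited form and should be corrected. Recorded times produced by a stent-graft, a different closure device or surgery enter the primary mean as MANTA's TTH, and any resulting bias favours the device. The expected size is a few tenths of a minute, against an assumed margin of 4 min. With 5 rescues and a longest value of 60 min the bound moves only from 7.72 to 8.62 min. Crossing 10 min needs several percent rescued together with a long maximum: about 4% and 60 min under the design assumptions, or about 4% and 120 min under EU-like values. Rescue counts, the 25 min rescue time and the maxima above 37 min are all assumptions. The working gives no ground for saying that the primary conclusion is likely to reverse, and the sample size is not in question.

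**What to change.** 1. In Protocol 8.3.3 and SAP 5.1 and 6.2.1, assign one stated unfavourable TTH to every subject whose arterial hemostasis was obtained by surgical repair, stent-graft or a different closure device, whether or not a time was recorded. Identify these subjects from the adjunctive-method field already summarized under SAP 6.2.3; a different closure device falls in its catch-all category, so those entries must be checked.
2. Use the longest TTH recorded for any Primary Analysis Cohort subject, in line with Protocol 8.3.3. Reconcile the same-site rule in Protocol 8.3.6 and SAP 5.1 with it; at a small site the worst value may be short.
3. Score these subjects as not a Treatment Success (Protocol Section 4, SAP 6.2.2).
4. Report the analysis on recorded times as a sensitivity analysis.
5. As a scoring clarification in Protocol 7.6, state that time under contralateral balloon occlusion counts in TTH as pressure time does. Balloon cases are not imputed.

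The cost is wording in both documents, settled before results are examined. No new data are needed and clinical care does not change. Mean TTH and Treatment Success become slightly less favourable to the device.
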